6 ADMINISTRATIVE RESPONSIBILITIES

6.1 Institutional Review Board (IRB)

This protocol and the informed consent must be reviewed and approved by each site's IRB prior to obtaining written informed consent or allowing a subject to participate. Changes to the protocol that may increase the risk or present new risks to the subject, or may adversely affect the validity of the trial, must be approved in writing by Sponsor, IRB and the FDA before the change is made.

IRB approval to participate in this trial is required from each institution participating in this investigation. Prior to subject enrollment, a signed copy of the IRB approval letter must be submitted to Sponsor certifying trial approval. Investigators are responsible for submitting and obtaining initial and continuing review (at intervals not greater than once a year) of the trial by their IRB.

The investigator will report to the Sponsor immediately, if, for any reason, the approval to conduct the investigation is withdrawn. The report will include a complete description of the reason(s) for which the approval was withdrawn.

6.2 Subject Informed Consent

Prior to screening for eligibility, subjects must consent to screening and baseline testing. During the consent process, the scope, and the description of tests of the screening and baseline should be reviewed with the subject. The subject should have the option to ask questions and have them answered to their satisfaction. The process of consenting the subjects must be documented on the screening and baseline informed consent form.

Prior to enrollment into the trial, subjects must consent to participate in the trial. During the consent process, the scope, requirements, risks and benefits of the trial should be reviewed with the subject. The subject should have the option to ask questions and have them answered to their satisfaction. The process of consenting the subjects must be documented on the Surgical Informed Consent Form.

The template Surgical Subject Informed Consent Form and Screening & Baseline Informed Consent Form for this trial is located in Attachment A. Any adaptation of this format must include the elements of Informed Consent as required by 21CFR Part 50. The Informed Consent used must be approved by the Sponsor and the Institutional Review Board (IRB) prior to its use.

A copy of the signed IRB approved Surgical Subject Informed Consent Form and Screening and Baseline Subject Informed Consent Form must be retained at the investigational site along with the other investigational forms. A copy of the consent form is to be given to the subject.

6.3 Confidentiality

All information and data sent to Sponsor concerning subjects or their participation in this trial will be considered confidential by the Sponsor. Only authorized Envoy Medical personnel and their designees (including contract research organizations), advisory committees, Investigators at other sites and IRBs will have access to these confidential files and have the right to inspect and copy all of the records pertinent to this trial. This may include medical information gathered prior to the onset of this trial. Authorized FDA personnel also have the right to inspect and copy all records pertinent to this trial. All data used in the analysis and reporting of this evaluation will be without identifiable reference to the subject.

Data collected and stored at the Sponsor will be free of identifying information of the subject including subject names and medical records numbers.

In order to comply with the Health Insurance Portability and Accountability Act (HIPAA) that became effective April 14, 2003 in the US all subjects enrolled in the trial will be required to provide authorization to disclose Protected Health Information (PHI).

6.4 Investigator Training

All investigators chosen to participate in the *Esteem® System* Post Approval Study are qualified by training and experience in otolaryngology therapy and surgery and have special expertise in the field of clinical research relating to the trial.

Sponsor will schedule training on the surgical procedure for each of the participating investigators.

Training will consist of a discussion of the scientific basis for the *Esteem® System*, indications for the device, pre-operative assessment of temporal bone CT scan, the sequence and positioning of the Driver and the Sensor. The training will include a discussion on the programmable features of the Sound Processor. Work in the temporal bone lab for hands on experience with the mastoidectomy; positioning the Sensor and Driver; and implantation of the *Envoy Sound Processor* will be included as part of training. Each participant will implant approximately 2 *Esteem® Systems* in temporal bones during training.

In addition, all site personnel will be trained on the clinical trial protocol, the CRF completion procedures, the regulations pertaining to conducting clinical trials, study processes, device handling, and the *Esteem® System* programmer.

The audiologists at each site will be trained on the use of the *Esteem®* Programmer. This training will include a discussion on the programmable features of the Sound Processor.

In addition, a representative from Envoy Medical will be present at all of the implant procedures to perform intra-operative testing and advise the investigators if needed, and at the initial clinical follow-ups to answer any questions and help set up the device program with the site audiologist.

All training will be documented in the clinical site files at the sponsor.

6.5 Investigators Responsibilities

In accordance with FDA regulation 21 CFR Part 812 the investigator is responsible for ensuring that the investigation is conducted according to this protocol and that signed informed consent is obtained from the subject prior to his inclusion in the study. It is the investigator's responsibility to ensure that all staff assisting with the trial have appropriate qualifications, are fully instructed on the trial procedures and will respect confidentiality.

6.6 Data Monitoring and Quality Control

6.6.1 Training

The training of appropriate clinical site personnel will be the responsibility of Sponsor. To ensure uniform data collection and protocol compliance, personnel from Sponsor will review the Investigational Plan, techniques for the identification of eligible subjects, instructions on data collection, methods for soliciting data from alternative sources, and schedules for follow-up with the research coordinator and audiologist.

6.6.2 Case Report Forms (CRFs)

CRFs will be used to collect all subject data during the trial. CRFs will be monitored following the guidelines established by Sponsor's Standard Operating Procedures (SOPs).

6.6.3 Data Reporting

All data should be recorded on the site's standard source documentation.

The investigator, or an individual designated by him/her, is responsible for transferring the information to the appropriate CRFs. The data on each CRF must be legibly handwritten with a blue/black ballpoint pen. The investigator is responsible for the quality of the data collected and recorded during the trial.

The investigator is required to sign the CRF on the appropriate page(s) to verify that he/she has reviewed the recorded data..

6.6.4 Data Review

All CRFs will be reviewed for completeness and clarity upon receipt by Sponsor. Missing or unclear data will be requested as necessary throughout the trial. Sponsor will request further documentation such as physician procedure notes when SAEs, and/or malfunctions are observed and reported.

Data entry and development of the primary database for the trial will be performed by Sponsor or their designee(s). Sponsor or designee(s) will also be responsible for auditing the database and confirming the overall integrity of the data.

Sponsor or designee will provide clinical monitoring, including review of CRFs and parity checks with the source documentation including operator worksheets retained with CRF documentation and hospital charts.

All clinical sites will be monitored routinely for timeliness of CRF submission to Sponsor. Any evident pattern of non-compliance with respect to the timeliness will initiate remedial actions. If corrective actions are not subsequently undertaken, the clinical site may be withdrawn.

To this end, the Principal Investigator must permit inspection of the trial files and subject CRFs by such representatives and/or responsible government agencies.

6.7 Record Maintenance

6.7.1 Records

Records to be maintained by the investigator in a designated clinical trial administrative file include:

- Clinical trial investigational plan and all amendments
- Signed clinical trial agreement
- IRB approval letter(s) including informed consent
- IRB membership list or compliance assurance statement
- Correspondence relating to the trial
- Curriculum Vitae (CVs) for all investigators (Principal and Co-investigator), audiologist and research coordinator
- Site personnel signature list
- Sponsor personnel sign-in log
- Blank sets of CRFs and instructions for completion
- Subject enrollment log
- Investigational device inventory log with invoices, including: date, quantity, serial numbers of all devices, and identification of all persons the device was used on (subject identification log)
- Log of all devices returned to the Sponsor and the reason for the return
- Device manual(s) and/or Instructions for Use (IFU)

7 REPORTS (INCLUDES ANNUAL REPORTS, FINAL REPORTS FROM INVESTIGATOR AND SPONSOR)

The following records must be maintained for each subject enrolled in the trial:

- Signed *Esteem® System* Subject Informed Consent Form
- All completed CRFs
- Record of and supporting documentation for any AEs.
- Procedure reports, nursing notes, and subject office files
- Records pertaining to subject death during the investigation (including death records, death certificate, and autopsy report, if performed)

Sponsor recommends that the investigator retain copies of procedure reports, procedure nursing notes, audiologist's reports and the results of any procedures that occur post trial procedure.

7.1.1 Reports

Investigators are required to prepare and submit to Sponsor complete, accurate and timely reports on this investigation when necessary.

Records and reports will remain on file for a minimum of two (2) years after the completion/termination of the investigational trial. They may be discarded upon notification by Sponsor. To avoid error, the principal investigator should contact Sponsor before the destruction of any records and reports pertaining to the trial to ensure they no longer need to be retained.

In addition, Sponsor should be contacted if the principal investigator plans to leave the investigational site so that arrangements can be made for transfer of records.

7.1.2 Investigator's Final Report

Upon completion or termination of the *Esteem® System* clinical trial, the principal investigator must submit a final written report to Sponsor and their IRB. The report must be submitted within three (3) months of completion or termination of the trial.

7.2 Investigational Site Monitoring Procedure

Envoy Medical will serve as the Sponsor of the *Esteem® System* clinical trial, and Envoy Medical or their designee will monitor the trial according to Envoy Medical's Standard Operating Procedures (SOPs) and specific FDA regulations.

7.3 Labeling: Instructions for Use

Copies of the proposed Instructions for Use for the *Esteem® System* are included as a separate document.

7.4 Deviations from Protocol

The investigator shall not deviate from the protocol without the prior written approval of Sponsor except in medical emergencies or in unforeseen, isolated instances where minor changes are made that will not increase the subject's risk or affect the validity of the trial. In medical emergencies, prior approval for protocol deviations will not be required, but Envoy Medical Personnel or their designee must be notified within five (5) working days of the incident. All protocol deviations must be documented as to the nature of the deviation and the reason for the deviation on the appropriate CRF.

7.5 Investigational Site Termination

Envoy Medical reserves the right to terminate an investigational site for any of the following reasons:

- Failure to secure subject informed consent
- Failure to report UADEs within 10 days of knowledge of the event
- Repeated protocol violations
- Repeated failure to complete case report forms
- Failure to enroll an adequate number of subjects
- Loss of or unaccounted for investigational product inventor

ATTACHMENT A: *Safety Algorithm*

Bone Conduction/Safety Algorithm

Introduction

Bone conduction (BC) using forehead probe placement will be the primary test for cochlear function stability. While forehead placement will minimize some of the test variability issues associated with the mastoid probe placement as detailed in IDE G000321, there remains the possibility that BC test-retest variability may result in test results outside the ± 10 dB limits due to equipment limitations and probe placement. As an improvement over the methods used in IDE G000321, the Safety Algorithm has been refined for use in this new clinical trial. In addition to bone conduction, the EnvoyGram function will be used as an in-situ audiogram to directly stimulate the cochlea. This method will be more accurate and a better indicator of cochlear stability than the previous EnvoyGram tests where testing done at implant was used to predict future performance.

The EnvoyGram IT

In addition to the programmable parameters used to affect the incoming signal, the Sound Processor has an internal tone generator that can be accessed through the *Esteem®* Programmer in a test mode called the EnvoyGram IT (EnvoyGram In-situ).

Simply put, the EnvoyGram IT is an in-situ audiogram utilizing the Driver to test cochlear function. When entering this test mode, the Sensor is deactivated. The *Esteem®* Programmer software allows the audiologists to select a frequency in the range 250 to 4000 Hz and amplitude in the range 55 to 119 dB SPL. The Sound Processor synthesizes and delivers a pure tone signal to the Driver to induce known vibrations directly into the cochlea. There are twelve steps of amplitude. Each step provides a 4 - 6 dB increase over the previous step. The typical EnvoyGram IT levels are based on:

- a. a typical intact chain displacement of 40 nm at 100 dB for frequencies below 1 kHz (Validated per ASTM F 2504 and EMC 003798-001),
- b. a typical Model 7502 Driver displacement in temporal bones of 88 nm/V (Validated per EMC 003798-001), and
- c. a typical SP tone output for each volume and tone setting (Validated per EMC 003788-101 and EMC 003872-001).

Each patient's intact chain has a unique displacement profile. During implant of the *Esteem®*, intact chain data is measured and recorded to provide a normalization factor for the EnvoyGram IT.

Intra-operative data, ASTM F 2504, and temporal bone studies at Envoy (i.e. EMC 003798-001) all indicate that patient-to-patient variability of intact chain displacement is at least ± 6 dB. ASTM F 2504 cites a 95% confidence interval of ± 6 dB in temporal bones. Clinical experience has also shown that accurately quantifying the intact chain displacement of each patient in a live surgical field is also limited to approximately ± 6 dB, due to presence of fluid in the middle ear space, available LDV laser angle, etc.

The EnvoyGram IT test protocol is similar to that of an audiogram. The intact-chain measurements are recorded on the Procedure and Discharge CRF (EMC 003900-003) and entered into the EnvoyGram IT by the audiologist. The test methodology is performed consistent with the Hughson-Westlake procedure. A signal is presented at the prescribed amplitude and frequency. If the subject acknowledges the signal, the intensity level is decreased two steps (10 - 12 dB). If that signal is not acknowledged, the intensity level is increased one step (6 dB), thus determining a threshold. This threshold provides a measure of cochlear function independent of the external auditory mechanism.

EnvoyGram IT SPL levels are customized to the patient by taking into account each patient's IC data. For instance, a patient with typical 40 nm IC displacement at 100 dB will have levels from 55 to 117 dB, but a patient with stiff 20 nm IC displacement at 100 dB will have levels from 61 to 123 dB. The table below lists the EnvoyGram levels for a) a typical intact chain displacement of 40 nm at 1.0 kHz, 100 dB SPL, b) an intact chain displacement of 20 nm at 1.0 kHz, 100 dB SPL, and c) an intact chain displacement of 80 nm at 1.0 kHz, 100 dB SPL.

[figure not shown]
Table 1: EnvoyGram IT levels in *Esteem®* Programmer after intra-operative IC data entry. EnvoyGram IT levels are listed in dB SPL and are automatically calculated in

the *Esteem®* Programmer for each patient's IC data collected during implant procedure. These are the levels available for each of the test frequencies.

Typical (40nm IC @ 100dB SPL)	34	40	46	52	58	64	70	76	82	88	94	100
Stiff (20nm IC @ 100dB SPL)	40	46	52	58	64	70	76	82	88	94	100	106
Loose (80nm IC @ 100dB SPL)	28	34	40	46	52	58	64	70	76	82	88	94

Since the EnvoyGram IT levels are calibrated to each patient, the "predicted" EnvoyGram IT thresholds are equal to the baseline pre-implant unaided audiogram for each test frequency. For instance, a patient with 55 dB baseline air conduction threshold at 1 kHz and 80 nm measured IC would have a predicted EnvoyGram IT of 58 dB at 1 kHz (first level above baseline unaided threshold of 55 dB).

Bone Conduction/Safety Algorithm

Safety Algorithm Explanation:

The first level of the safety algorithm will use standard bone conduction (BC) thresholds. Bone conduction thresholds are measured in the implanted ear at 0.5, 1.0, 2.0, and 4.0 kHz at baseline and follow-up visits. If less than two (2) of the follow-up thresholds are more than 10 dB greater than the baseline thresholds, then the individual test frequencies are evaluated. At each test frequency, if the follow-up threshold is less than 20 dB greater than the baseline threshold then the algorithm is considered complete, with a conclusion that no change cochlear function occurred. However, if at least two (2) of the thresholds have increased more than 10 dB or if any individual threshold has increased by 20 dB or more, then the EnvoyGram data is evaluated.

The second level of the safety algorithm will use EnvoyGram thresholds. Baseline unaided air conduction pure tone thresholds at 0.5, 1.0, 2.0, and 4.0 kHz are measured at baseline. Similarly, EnvoyGram thresholds are measured in the implanted ear at 0.5, 1.0, 2.0, and 4.0 kHz at follow-up visits. Based on the intra-operative intact chain data, an EnvoyGram equivalent dB threshold is calculated for each of the four test frequencies. If less than two (2) of the follow-up EnvoyGram thresholds are more than 10 dB greater than the baseline thresholds, then the individual test frequencies are evaluated. At each test frequency, if the follow-up EnvoyGram threshold is less than 20 dB greater than the baseline threshold

then the algorithm is considered complete, with a conclusion that no change in cochlear function occurred. However, if at least two (2) of the EnvoyGram thresholds have increased more than 10 dB or if any individual EnvoyGram threshold has increased by 20 dB or more, then the algorithm is considered complete with a conclusion that a change in cochlear function occurred.

For patients with moderate to severe sensorineural hearing loss, non-responses (NR) are not uncommon during bone-conduction testing. If an NR occurs during baseline bone conduction testing, that test frequency is not evaluated (for the same patient) in the follow-up bone conduction portion of the safety algorithm. However, if an NR occurs during follow-up bone conduction testing (and is not preceded by a baseline NR at the same test frequency), the corresponding EnvoyGram threshold is substituted at the bone conduction NR test frequency.

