2. To demonstrate that the *Esteem® System* is as effective as or better than the hearing aid for improving speech discrimination (intelligibility) as shown by the word recognition score at 50 dB.

Endpoint: Comparison of the word recognition score using the *Esteem®* compared to the pre-implant aided condition.

3. To determine the incidence of Serious Adverse Device Effects (SADE) and Adverse Device Effects (ADE) and the incidence rate of device failures and replacements.

Endpoint: The analysis of the incidence of SADEs and device failures and replacements at each follow-up.

4. To demonstrate that the incidence of facial pareses/paralysis is no greater than the 7% incidence experienced in the PMA clinical trial.

Endpoint: The analysis of the incidence of facial pareses/paralysis at 1 month follow-up.

5. To demonstrate that the subjects' cochlear function remains unchanged with the *Esteem® System* as shown by comparison of the subjects' pre-implant baseline bone conduction threshold versus the subjects' post-activation visit bone conduction threshold.

Endpoint: Comparison of bone conduction threshold (BC) using forehead placement post activation compared to the pre-implant BC threshold.

Secondary Objectives:

1. To show that the *Esteem® System* improves Quality-of-Life when compared to the baseline aided condition as shown by APHAB results.
2. To gather subject feedback and comments on the use of the *Esteem® System* relative to the pre-implant hearing aid (aided condition) as shown by the *Esteem® Questionnaire*.

Sponsor Contact Information:

Envoy Medical Corporation, Inc. (EMC)

[name]

[name]

[contact]

Customer Service [contact]

www.envoymedical.com

Changes in Revision 04

Change footer revision number from Rev 03 to Rev 04
Clarify the enrollment totals for efficacy and safety endpoints in Protocol Summary, sections 1.4, 2.2 and 4.7
Change sponsor address of Envoy Medical Corporation to current address
Miscellaneous typo corrections

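### A frequency with no response at baseline bone conduction leaves the first level of the safety algorithm with no substitute, so an ear can be concluded unchanged while its EnvoyGram there goes unread

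*Combined protocol and SAP*

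**What the plan says.** Primary Objective 5 is that cochlear function stays unchanged. Its endpoint in the Protocol Summary is "Comparison of bone conduction threshold (BC) using forehead placement post activation compared to the pre-implant BC threshold". Section 5.2 gives the safety algorithm as the analysis for BC results outside the stability range. It calls the algorithm Attachment C, but the text stands under Attachment A.

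Attachment A sets out these steps:

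- **Role of BC.** "Bone conduction (BC) using forehead probe placement will be the primary test for cochlear function stability".
- **Level 1.** BC is compared with baseline at 0.5, 1, 2 and 4 kHz. If at least two thresholds are worse by more than 10 dB, or "if any individual threshold has increased by 20 dB or more, then the EnvoyGram data is evaluated". If neither holds, the algorithm is complete and the conclusion is no change.
- **Level 2.** The same rule is applied to EnvoyGram against baseline unaided air conduction, and "an EnvoyGram equivalent dB threshold is calculated for each of the four test frequencies".
- **NR at baseline BC.** "that test frequency is not evaluated (for the same patient) in the follow-up bone conduction portion of the safety algorithm".
- **NR at follow-up BC only.** "the corresponding EnvoyGram threshold is substituted at the bone conduction NR test frequency", provided there was no baseline NR at that frequency.

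On frequency of occurrence, the attachment says only that "non-responses (NR) are not uncommon during bone-conduction testing" in this population.

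**The concern.** Level 1 is the only gate to level 2. A baseline-NR frequency is taken out of the gate and nothing replaces it, so it cannot help to open level 2. An ear whose shift lies at such frequencies leaves the algorithm as unchanged without anyone having looked there. The plan treats a follow-up NR differently: there the EnvoyGram stands in.

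The error runs one way. An unexamined frequency can only move an ear toward no change, which favours the device on a primary safety objective. Section 4.7.1 lists failure of the algorithm among adverse events, so the ear also loses that route to being recorded as one.

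**Working it through.** The plan states no figure on this point, so there is none to reproduce. The check is of the decision rule.

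**Inputs.** Four frequencies; change rule = (two or more shifts above 10 dB) or (any shift of 20 dB or more); the NR rules above (all Attachment A). EnvoyGram is scheduled at activation and at 1, 4 and 10 months, and air conduction at baseline (Section 4.6, Table 1).

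**Step 1: routes to level 2.** Attachment A gives one, the level 1 trigger on evaluable BC frequencies. Section 5.2 gives no other, since it too applies the algorithm to BC results outside the stability range. With *k* baseline NRs, 4 − *k* frequencies can trigger. For *k* = 3 one remains, so two shifts above 10 dB are impossible and only the 20 dB arm is left. For *k* = 4 nothing remains, and no outcome is stated.

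**Step 2: example ears (order 0.5, 1, 2, 4 kHz).**

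- BC shifts 0/0/NR/NR, EnvoyGram shifts 0/0/30/30 dB: level 1 sees 0/0, so no change. Level 2 would call the same EnvoyGram values a change.
- Baseline NR at 4 kHz, shifts of 15 dB at 2 and 4 kHz: one evaluable shift above 10 dB, so no change.
- Baseline NR at 4 kHz with a 30 dB shift there, and 15 dB at 1 and 2 kHz: the remaining frequencies trigger, level 2 is reached, change.

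**Step 3: placements.** Let *m* frequencies be shifted and *k* be baseline NR, with C(4,*m*)·C(4,*k*) placements. Those leaving *j* shifted frequencies evaluable number C(4,*m*)·C(*m*,*m*−*j*)·C(4−*m*,*k*−*m*+*j*). With 15 dB shifts an ear is missed if *j* < 2; with 30 dB shifts, if *j* = 0. For example, 15 dB, *m* = 2, *k* = 2: *j* = 0 gives 6·1·1 = 6 and *j* = 1 gives 6·2·2 = 24, so 30 of 36.

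| Shift | *k* = 1 | *k* = 2 | *k* = 3 |
|---|---|---|---|
| 15 dB at two | 12 of 24 | 30 of 36 | 24 of 24 |
| 30 dB at one | 4 of 16 | 12 of 24 | 12 of 16 |
| 30 dB at two | 0 of 24 | 6 of 36 | 12 of 24 |
| 15 dB at all four | 0 of 4 | 0 of 6 | 4 of 4 |

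Every placement counted here meets the change rule on all four frequencies. The counts show how the rule behaves; they are not rates.

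**Step 4: how far an EnvoyGram shift can be trusted alone.** The typical row of the EnvoyGram table runs from 34 to 100 dB in 6 dB steps. The attachment's example takes the predicted level as the "first level above baseline unaided threshold of 55 dB". Read literally, one step above prediction already exceeds +10 dB at 4 of 13 five-dB baselines from 30 to 90 dB: 35→40→46 (+11), 40→46→52 (+12), 65→70→76 (+11), 70→76→82 (+12). Read as at or above, it does so at 2 of 13 (35 and 65).

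Attachment A also puts intact-chain measurement error at about ±6 dB. The predicted level is never below baseline, so a +6 dB error plus one 6 dB step gives at least +12 dB (for instance 55→58→64→70, +15). If that error is shared across an ear's frequencies, two baseline NRs could meet the rule with no cochlear change.

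**Step 5: EnvoyGram NR.** The plan does not say how to score one. For an 85 dB baseline and a typical chain, the ceiling is 100 − 85 = +15 dB by the table, but 117 − 85 = +32 or 119 − 85 = +34 dB by the text.

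**The case against.** BC is the stated primary test, the endpoint is a BC comparison, and a baseline NR leaves nothing to subtract from. EnvoyGram works through the Driver and assumes a typical Driver displacement. Section 4.5.2 expects that a revision may be needed to attach the Driver properly to the stapes, so poor coupling could raise EnvoyGram thresholds with no cochlear change. Requiring BC to trigger first protects against that. Step 4 adds step size and calibration error.

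Much of this stands. It justifies not comparing BC at a baseline-NR frequency, and not letting EnvoyGram alone produce a finding of change. It does not justify the opposite conclusion, no change, for an ear whose EnvoyGram was collected but not read.

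Three stronger readings are tempting, and the documents do not support them:

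- **That a missed ear goes unrecorded as an adverse event.** Section 4.7.1 defines adverse events broadly, including a change in the subject's condition. Only the algorithm-based route is lost. Adverse events, aided speech tests and air conduction are collected at each visit from activation.
- **That a 0/0/30/30 EnvoyGram pattern proves cochlear loss.** Coupling or calibration could produce it.
- **That the table in the working gives the share of ears misclassified.** It weights placements equally, and the documents give no NR rate.

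**Conclusion.** The gap is real and follows from the text alone. As written, an ear with a shift confined to, or dependent on, baseline-NR frequencies is concluded unchanged unless its remaining BC frequencies trigger by themselves, and an ear with four baseline NRs has no stated outcome. The Objective 5 count is biased toward unchanged.

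The size in ears cannot be given. It depends on how often baseline NR occurs and on where shifts fall. Objective 5 has no numeric success criterion, so no pass or fail result turns on it; what suffers is the reported count. It should be fixed, because the data to close the gap are already scheduled.

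The placement counts assume no measurement error, and an EnvoyGram shift equal to the true shift wherever EnvoyGram is used. The reading of the rule needs neither assumption.

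**What to change.** Replace the baseline-NR sentence in Attachment A with:

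> A frequency with NR at baseline BC is not compared by BC. For any ear with one or more such frequencies that does not meet the level 1 trigger on its remaining frequencies, the EnvoyGram shift from baseline unaided air conduction is read at all four frequencies. If the level 2 change rule is not met and all four EnvoyGram thresholds are measurable, the ear is reported as no change (by EnvoyGram at baseline-NR frequencies). If the rule is met, the ear is reported in a separate category: possible change on EnvoyGram alone, without BC corroboration. If an EnvoyGram NR leaves the rule undetermined, the ear is reported as not fully evaluable. Neither of the last two categories is counted as no change.

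Report the counts by number of baseline NRs (1, 2, 3, 4), with the classification under the present Attachment A text alongside, so that a reader sees how many ears move. If the EnvoyGram shift equals the loss, every missed placement in the table moves to the separate category and none is counted as unchanged; the same holds with four NRs.

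**Cost.** Attachment wording and derivation code; no new test. Because the algorithm also underlies a listed adverse event, the amendment should say whether the new category counts as a failure of the algorithm under Section 4.7.1, and should be checked against the approval requirement in Section 6.1. The new category will include some ears with coupling or calibration artefacts, or with EnvoyGram shifts at frequencies where BC was stable. That is why it stays separate; listing the frequencies that met the rule would show this.

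Do not score an EnvoyGram NR by ceiling until the ranges in the text (55 to 117 or 119 dB typical, 61 to 123 dB stiff) are reconciled with the table (34 to 100 and 40 to 106 dB). That is a separate issue, and the wording above does not depend on it.
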